- Second packet reconstituted and administered the next day (day of colonoscopy) at least 5 hours, but no more than 9 hours, prior to the colonoscopy

DURATION OF TREATMENT

Treatment and follow-up: 2-day treatment and four week follow-up.

TRIAL PROCEDURES / ASSESSMENTS

Visit	1 Screening	2 Randomization	3 Procedure	4 Follow-up	5 Follow-up	6 Follow-up (EOT)
Timing versus Procedure	≤21 Days	≤10 Days	Colonoscopy (T = 0)	1-2 Days	7 Days (± 2 Days)	4 Weeks (± 2 Days)
Informed consent	x					
Inclusion/exclusion criteria	x	x				
Demographic & Medical History	x					
Body weight, Height ¹	x	x	x	x	x	x
Urine/Serum Pregnancy Test	x	x ⁷				
Schedule colonoscopy	x					
Laboratory (chemistry, coagulation, hematology)	x ²		x	x	x	x
PK sampling			x ^{3,4}			
Urinalysis	x		x ⁵	x	x	x
ECG	x		x	x	x	x
Physical examination	x		x	x	x	x
Orthostatic vital signs (BP, pulse)	x	x	x	x	x	x
Concomitant medications	x	x	x	x	x	x
Adverse events	x	x	x	x	x	x
Dispense fluid intake diary and study medication		x				
Subject Tolerability Questionnaire			x			
Perform and video-record colonoscopy			x			
Score overall colon preparation – Modified Aronchick scale			x			
Score colon segments preparation – Boston Bowel Preparation Scale			x			
Drug accountability ⁶			x			

-
1. Height will only be collected at screening.
 2. Coagulation samples will only be collected at screening.
 3. In a subset of subjects, PK samples for sodium picosulfate and BHPM will be taken 15 minutes before the second dose, and 1 to 2 hours and 3 to 6 hours after the second dose of the Sodium Picosulfate, Magnesium Oxide and Anhydrous Citric Acid.
 4. All subjects will have a PK sample drawn immediately prior to colonoscopy (approximately 2 hours prior to the colonoscopy).
 5. At the colonoscopy visit, the urinalysis panel will include urine osmolality.
 6. Drug accountability will be performed by an unblinded coordinator or unblinded pharmacist (if applicable) and an unblinded monitor only.
 7. Premenopausal women of childbearing potential must have a urine pregnancy test performed within 3 days prior to colonoscopy. For women of childbearing potential **randomization must occur within 3 days prior to colonoscopy**
-

STATISTICAL METHODS

Sample Size Calculation

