7.2.3 Clinical Laboratory Variables

All laboratory measurements will be performed using appropriately validated methods by a central laboratory selected by the Sponsor. Sample handling and storage will be provided to all sites directly from the central laboratory.

Laboratory values will be reported to the Investigator and Sponsor (or the Sponsor's representative) and will automatically be uploaded to a database. The database will be maintained by a clinical research organization selected by the Sponsor.

Out of range values will be described in the laboratory manual to be provided by the central laboratory. Investigators will assess all out of range values as being either clinically significant or not clinically significant via the eCRF. Clinically significant abnormal laboratory measurements should be reported as AE.

Sites will be specially instructed to review all laboratory results in order to determine if the subject is eligible for study participation and to determine any adverse events post study drug administration.

Sites will be provided with sampling supplies and materials for shipment and a manual detailing all sample collection and shipment procedures.

Following Screening Visit (V1, see Section 6.1), subjects with clinically significant abnormal laboratory values will not be randomized into this study.

The following values will be collected and sent out to the central laboratory at all study visits except the randomization visit.

- Hematology panel:
 - Full CBC and differential
- Full chemistry panel:
 - Serum Chemistry: serum osmolality, bicarbonate, fasting glucose, blood urea nitrogen (BUN), creatinine, magnesium, potassium, sodium, chloride, calcium, protein total, albumin, bilirubin total, alkaline phosphatase, aspartate aminotransferase (AST), alanine aminotransferase (ALT), and gamma glutamyl transferase (GGT)
 - Calculated creatinine clearance and BUN/creatinine ratio
- Urinalysis panel (at the colonoscopy visit (V3), this includes urine osmolality)

The following values will be collected at the site during the Screening Visit only (see Section 6.1):

- Serum pregnancy test for premenopausal female subjects
- Coagulation Panel:
 - PT, APTT

The following value will be collected during Randomization Visit only (V2, see Section 6.2):

- Urine pregnancy test (onsite) for premenopausal female subjects

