8 ADVERSE EVENTS

8.1 Adverse Event Definition

An adverse event is any untoward medical occurrence in a subject participating in a clinical trial. It includes:

- Any unfavourable and unintended sign, symptom, or disease, whether or not considered to be caused by the IMP
- Adverse events commonly observed and adverse events anticipated based on the pharmacological effect of the IMP
- Any laboratory abnormality, vital sign, or finding from physical examination assessed as clinically significant by the Investigator. [Note: pre-existing conditions diagnosed through assessments and examinations at the Screening Visit (V1, see Section 6.1) or during the screening period are not adverse events, but are recorded as medical history]
- Accidental injuries, reasons for any change in medication (drug and/or dose), reasons for any medical, nursing, or pharmacy consultation, or reasons for admission to hospital or surgical procedures
- Overdoses and medication errors with and without clinical consequences

An adverse drug reaction (ADR) is an AE evaluated by the investigator as having a reasonable possibility of being related to treatment with the IMP.

A serious ADR is a serious adverse event (SAE) evaluated by the investigator and/or by Ferring as having a reasonable possibility of being related to treatment with the IMP.

An unexpected AE is an AE not identified in nature, severity, or frequency in the section “Undesirable Effects” in the sponsor’s current Investigator’s Brochure and current approved label.

A treatment-emergent AE is any AE that begins during the treatment period, or is a worsening of a pre-existing medical condition. The treatment period is defined as the period during which a subject receives IMP.

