9.8.3 Safety Laboratory Variables

All safety laboratory values outside normal range will be listed separately by subject number, including demographic information and flagging values.

Continuous laboratory safety data will be summarized by treatment group and scheduled time point using descriptive statistics: sample size, mean, median, standard deviation, minimum, and maximum values. Changes from baseline will be summarized in the same way.

Categorical laboratory safety data will be summarized separately by treatment group and scheduled time point using the number and percentage of subjects in each category.

The incidence of clinically significant changes in laboratory values will be summarized separately by treatment group and scheduled time point.

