### 10.3 Safety Laboratory Variables

Baseline for all laboratory analyses will be the values obtained at the last assessment prior to the first dose of the investigational medicinal product (IMP). Treatment-emergent laboratory data will include tests completed after the first dose of IMP. End of trial assessment will include the last post-baseline observation during the trial.

Laboratory variables will be grouped under “Haematology”, “Clinical Chemistry” or “Urinalysis”

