### 10.3.2 Laboratory Variable Changes Relative to Normal Range

Changes relative to normal ranges are presented with shift tables with total number of subjects, and number and percent of subjects who experienced a shift by treatment group. The following categories for shift tables are defined:

- Low: Values which are below the lower reference range limit;
- Normal: Values which are within the lower and upper reference range;
- High: Values which are above the upper reference range limit.
- Absent: No value for measured variable (for urinalysis only)
- Present: Any value obtained for measured variable (for urinalysis only)

For all haematology and clinical chemistry variables, shift tables will be prepared to compare baseline values to the worst in-treatment value. More specifically, for haematology and clinical chemistry, tables presenting the changes from *Low* or *Normal* to *High* and from *High* or *Normal* to *Low* will be provided. For urinalysis variables, shift tables will summarise the number (%) of subjects who had “absent” values at baseline and “present” values during the treatment period.

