### 10.3.4 Urinalysis

Categorical urinalysis laboratory data will be summarized separately by treatment group and scheduled time point using the number and percentage of subjects in each category. Furthermore, incidence of changes in urinalysis will be summarised by treatment group. A summary table with number of subjects with change from *Absent* at baseline to *Present* during trial will be summarised.

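### The chemistry and haematology shift table has no visit dimension, so it cannot show how many subjects per arm left the normal range around the preparation

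*SAP*

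**What the plan says.** SAP 10.3.2 defines Low, Normal and High against the reference range. For every haematology and chemistry variable, "shift tables will be prepared to compare baseline values to the worst in-treatment value". The counts are of moves into High from Low or Normal, and into Low from High or Normal. No visit is named.

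SAP 10.3 sets the post-dose window: "Treatment-emergent laboratory data will include tests completed after the first dose of IMP". It gives no upper limit. The protocol synopsis describes "2-day treatment and four week follow-up", and Protocol 7.2.3 has haematology, chemistry and urinalysis "collected and sent out to the central laboratory at all study visits except the randomization visit". That gives a screening draw and four post-dose draws: Visit 3 (day of colonoscopy), Visit 4 (1-2 days), Visit 5 (7 days) and Visit 6 (4 weeks).

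Protocol 9.8.3 plans three summaries by arm and scheduled time point:
- numeric data: "Continuous laboratory safety data will be summarized by treatment group and scheduled time point using descriptive statistics";
- categorical data: "Categorical laboratory safety data will be summarized separately by treatment group and scheduled time point using the number and percentage of subjects in each category";
- clinically significant changes: how often they occur.

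In the SAP, 10.3.1 gives observed values and change from baseline at each visit, 10.3.3 lists abnormal values, and 10.3.4 says "Categorical urinalysis laboratory data will be summarized separately by treatment group and scheduled time point".

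**The concern.** The safety question in this trial is short-lived. Two formulations of the same actives are taken over two days, and any disturbance of electrolytes, osmolality or renal function is most likely to appear in the Visit 3 draw, hours after the second dose, or at Visit 4. A table of the worst value over Visits 3 to 6 adds incidental out-of-range values from up to four weeks later to both arms, and it does not date the shift. Means by visit do not fill the gap, because they do not give a count, with a denominator, of subjects who left the normal range at a given visit. A small group with a clear shift can leave the mean almost unchanged.

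Clinically significant laboratory changes are also part of a secondary endpoint (SAP 2.2), so how they are tabulated by visit should be explicit.

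**Working it through.** **1. Which visits does in-treatment cover?** The term is not defined, so the related wording has to be compared.

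| Place | Points to |
|---|---|
| SAP 10.3, every test after the first dose is treatment-emergent | Visits 3-6 |
| SAP 7.3, treatment period for concomitant medication extends to Visit 6 | Visits 3-6 |
| SAP 10.3.2 and 10.3.4, the same urinalysis shift is placed in the treatment period in one and during the trial in the other | Visits 3-6 |
| Protocol 8.1: "The treatment period is defined as the period during which a subject receives IMP" | Visit 3 only |
| SAP 10.4.2.2, separates ECGs during treatment from those after it | a narrower window |

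A worst value also presupposes more than one value, and the narrow reading leaves only one scheduled draw. The SAP's usage favours Visits 3-6 but does not settle it. On the narrow reading there is no dilution, but Visits 4-6 then have no chemistry or haematology shift count at all.

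**2. Protocol 9.8.3 against the SAP.**

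| Protocol item, by time point | SAP counterpart |
|---|---|
| Numeric data, descriptive | 10.3.1, all laboratory variables |
| Categorical data, n (%) | 10.3.4, urinalysis |
| Incidence of clinically significant changes | none in 10.3; not declared in SAP 12 |

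**3. Number per arm.** The documents give no figure for the shift tables. The only planned figure used is 450 per arm (SAP 3.2). It reproduces: n = (1.960 + 1.282)² × 2 × 0.84 × 0.16 / 0.08² gives 442 per arm for 90% power, and 450 gives 90.5%.

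**4. Size of the dilution.** The rates below are assumptions, since the documents give none. Let q be the chance of a counted out-of-range value in one direction at one visit, with a 3-point excess in one arm at Visit 3 only and visits independent. Over k visits:

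- unaffected arm: p2 = 1 − (1 − q)^k
- affected arm: p1 = 1 − (1 − q − 0.03)(1 − q)^(k−1)
- z = (p1 − p2) / √{[p1(1 − p1) + p2(1 − p2)] / 450}

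| q | Visit 3 alone (k = 1) | Worst of Visits 3-6 (k = 4) | Ratio of z² |
|---|---|---|---|
| 2.5% | 5.5% vs 2.5%, z = 2.30 | 12.4% vs 9.6%, z = 1.33 | about one third |
| 1% | 4.0% vs 1.0%, z = 2.90 | 6.9% vs 3.9%, z = 1.94 | about 45% |

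The difference itself shrinks only by the factor (1 − q)³. At q = 2.5% that is 0.927, so 3.0 points becomes 2.8. Most of the fall in z comes from the larger variance at higher base rates.

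A second case takes 10% vs 15% at Visit 3 (z = 2.27, power 62%) and a background rate b at each of Visits 4-6:

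| b | Worst of Visits 3-6 | Difference | z | Power | Affected-arm cases not abnormal at Visit 3 |
|---|---|---|---|---|---|
| 1% | 12.7% vs 17.5% | 4.9 points | 2.04 | 53% | 14% |
| 2.5% | 16.6% vs 21.2% | 4.6 points | 1.78 | 43% | 29% |
| 5% | 22.8% vs 27.1% | 4.3 points | 1.49 | 32% | 45% |
| 10% | 34.4% vs 38.0% | 3.6 points | 1.14 | 21% | 61% |

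z and power are only gauges of visibility, because SAP 10.1 plans no safety tests. With fully dependent visits (the same subjects out of range at every draw) the worst-value rate equals the single-visit rate and nothing is lost.

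**The case against.** A reader might infer that the SAP replaced a protocol table of Low/Normal/High counts by visit. The documents do not support this. Protocol 9.8.3 separates numeric from categorical laboratory data and defines no such categories for chemistry or haematology, whose analytes are nearly all numeric. SAP 10.3.1 delivers the numeric part and 10.3.4 the urinalysis part. The shift table is an addition, so SAP 12 had nothing to declare about it. That objection stands. It does not cover the incidence of clinically significant changes, which the protocol does ask for by time point.

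The arithmetic is also open to challenge. Independent visits are an unfavourable assumption, because repeated values in one subject are usually correlated. The shift counts leave out subjects already out of range in that direction at baseline, which removes stable background abnormality. At 2.5% background, 93% of the difference survives. All of this stands, and it is why the figures are illustrations and not estimates. None of it gives the table a time axis.

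Finally, the table shells are in a separate document (SAP 14) and may show more. The SAP text should still carry the rule.

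**Conclusion.** The point holds as an inexpensive improvement to descriptive safety reporting. It does not touch the primary or right-colon analyses. As written, the shift table has no visit dimension and its window is undefined. On the reading the SAP favours, it mixes the Visit 3 draw with three follow-up draws and gives no count per arm of subjects leaving the normal range around the preparation.

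It would be tempting to conclude that a Visit 3 effect would be buried. That goes too far. SAP 10.3.1 gives mean, SD, median, minimum and maximum by arm at Visit 3, and SAP 10.3.3 lists abnormal values. Protocol 7.2.3 has clinically significant abnormalities reported as adverse events, Protocol 8.2.2 dates their onset to the sample, and SAP 10.2.2 tabulates them by arm. The effect is diluted and untimed in one table. The dilution runs from none (fully dependent visits, or in-treatment meaning Visit 3 only) to a loss of roughly half to two thirds of the information in the 3-point example (independent visits, 1% to 2.5% background).

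The one clear gap against the protocol is the by-time-point incidence of clinically significant laboratory changes.

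**What to change.** 1. In SAP 10.3.2, state which visits in-treatment covers.
2. Add Low/Normal/High shift counts from baseline by arm at each of Visits 3, 4, 5 and 6. Use as denominator the subjects with a baseline value and a value at that visit. Keep the worst-value table as a supplement.
3. Add the incidence of clinically significant laboratory changes by arm and scheduled time point, as planned in Protocol 9.8.3, or declare and explain its omission in SAP 12.

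No new data are needed. The draws are already scheduled, and Protocol 7.2.3 has investigators record clinical significance in the eCRF. The cost is a loop over visits in the table program and more pages of output.

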### 10.3.3 Data Listings

Data listings will be prepared by treatment group and site for all subjects with any abnormal or markedly abnormal laboratory value at any time-point (including screening, baseline). The pre-specified markedly abnormal criteria are presented in [Appendix 1](#) Appendix 1 .

### 10.3.4 Urinalysis

Categorical urinalysis laboratory data will be summarized separately by treatment group and scheduled time point using the number and percentage of subjects in each category. Furthermore, incidence of changes in urinalysis will be summarised by treatment group. A summary table with number of subjects with change from *Absent* at baseline to *Present* during trial will be summarised.

## 10.4 Vital Signs and ECG

### 10.4.1 Vital Signs

Baseline for all vital signs (sitting, supine or orthostatic) analyses will be the values obtained at the last assessment prior to the first dose of IMP. Treatment-emergent vital signs data will include tests completed after the first dose of IMP. Last assessment in the study will include the last post-baseline observation during the trial.

Observed and change from baseline values for standing, supine and orthostatic vital signs will be summarized by visit and for the last assessment in the study. For orthostatic vital signs only observed values will be summarized. The orthostatic blood pressure and pulse to be summarized are the change in these measures from supine position to standing position. In this study, BP and pulse, will be first measured after at least 5 minutes rest in supine position and after 3 minutes in standing position.

Orthostatic vital signs cut off that are suggestive of fluid volume depletion are as follows [14]:

- a decrease in systolic blood pressure greater or equal to 20 mmHG within 3 minutes of standing,
- a decrease in diastolic blood pressure greater or equal to 10 mmHG within 3 minutes of standing, or
- increase in heart rate (pulse rate) greater or equal to 30 beats per minute (bpm) in the presence of drop blood pressure.

At each visit the number of patients, with such changes in orthostatic vital signs will be summarized by treatment arm.

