9.8.4 Other Safety Variables

9.8.4.1 Vital Signs

Each vital sign will be summarized by treatment group and scheduled time point using descriptive statistics: sample size, mean, median, standard deviation, minimum, and maximum values. In addition changes from pre-treatment will be summarized in the same way.

The incidence of clinically significant changes in vital signs will be summarized separately by treatment group and scheduled time point.

The incidence of markedly abnormal changes in vital sign values will be summarized by treatment group.

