#### **10.4.1.1 Summary Statistics**

For each vital signs variable at each visit the assessments will be summarized by treatment arm. The summary includes descriptive statistics such as the number of subjects with data, mean (standard deviation), median, minimum, and maximum values, for observed values and change from baseline at each time-point for each vital signs variable. Change from baseline values will not be summarized for orthostatic vital signs.

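### SAP 10.4.1 gives opposite instructions on orthostatic change from baseline, and its fluid-depletion count does not separate new-onset from pre-existing cases

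*SAP*

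**What the plan says.** SAP 10.4.1 defines a baseline, before the first study-drug intake, that names orthostatic values: "Baseline for all vital signs (sitting, supine or orthostatic) analyses will be the values obtained at the last assessment prior to the first dose of" [...]. It then states: "Observed and change from baseline values for standing, supine and orthostatic vital signs will be summarized by visit". The next sentence reads: "For orthostatic vital signs only observed values will be summarized". The variable is then defined: "The orthostatic blood pressure and pulse to be summarized are the change in these measures from supine position to standing position". SAP 10.4.1.1 closes with: "Change from baseline values will not be summarized for orthostatic vital signs".

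SAP 10.4.1 also lists cut-offs for falls in systolic and diastolic pressure and for a rise in pulse on standing, described as suggestive of fluid volume depletion. It adds: "At each visit the number of patients, with such changes in orthostatic vital signs will be summarized by treatment arm". No condition on baseline status is attached.

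Protocol 9.8.4.1 says: "Each vital sign will be summarized by treatment group and scheduled time point using descriptive statistics", and then: "In addition changes from pre-treatment will be summarized in the same way". SAP 12, which lists departures from the protocol analysis, mentions for vital signs only the removal of the markedly abnormal summary table.

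**The concern.** There are two linked problems.

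First, consecutive sentences tell the programmer to produce and not to produce the same summary. Following the restriction leaves the orthostatic part of the baseline definition without a use in these summaries and drops an analysis that can be read into the protocol. SAP 12 does not record the choice.

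Second, the cut-off table is meant to show possible volume depletion after a bowel preparation, but it counts everyone who meets a cut-off at a visit. A subject with the same drop on standing at Visit 2 and Visit 3 appears as a post-dose case. Such subjects can enter the trial: under Protocol 4.1.2, severe dehydration and abnormal vital signs exclude only on the investigator's judgement, and no criterion names an orthostatic drop. The SAP does condition on baseline elsewhere: in the laboratory shift tables (10.3.2), in the urinalysis absent-to-present table (10.3.4), and in the markedly abnormal vital-sign criteria (Appendix 1, Table 3).

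At stake is how clearly a descriptive safety table shows a difference between formulations. The arms also have different clear-liquid instructions after the second dose (Protocol 3.1.2), which makes a clean view of this contrast useful.

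**Working it through.** **Part 1: what each text asks for**

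| Quantity | SAP 10.4.1, general sentence | SAP 10.4.1, next sentence, and 10.4.1.1 | Protocol 9.8.4.1 |
|---|---|---|---|
| Supine values, change from baseline | yes | not restricted | yes |
| Standing values, change from baseline | yes | not restricted | yes |
| Supine-to-standing difference, change from baseline | yes | no | not named as a variable |

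Protocol 7.2.2 uses the term orthostatic vital signs for blood pressure and pulse measured supine and standing. Both positions keep their change from baseline, so the conflict is confined to the third row.

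**Part 2: the cut-off count**

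The plan gives no figure for this table. The only design figure used is the arm size, which reproduces. For 84% in both arms, an 8-point margin, one-sided 0.025 and 90% power, n = 2 × 0.84 × 0.16 × (1.960 + 1.282)² / 0.08² ≈ 442 per arm, against 450 stated. Power at 450 is 90.5%.

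Notation:
- b: fraction meeting a cut-off at the last pre-dose assessment, equal in both arms on average through randomisation.
- s: post-dose rate among those subjects.
- e: new-onset rate among the rest.

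The all-subject rate in arm i is P_i = b·s_i + (1 - b)·e_i. The between-arm difference is therefore

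RD_all = (1 - b)(e_1 - e_2) + b(s_1 - s_2).

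- If s is the same in both arms (full persistence, s = 1, is one case), RD_all = (1 - b)(e_1 - e_2).
- If baseline status is uninformative (s_i = e_i), RD_all = e_1 - e_2 and nothing is lost.

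The documents give no value for b, s or e, so all three are assumptions. With e = 10% in one arm and 5% in the other, a new-onset count shows a difference of 5.0 points and a ratio of 2.00. The all-subject count shows:

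| b | Rates, s = 1 | Difference (points) | Ratio, s = 1 | Ratio, s = 0.5 |
|---|---|---|---|---|
| 2% | 11.8% vs 6.9% | 4.9 | 1.71 | 1.83 |
| 5% | 14.5% vs 9.75% | 4.75 | 1.49 | 1.66 |
| 10% | 19.0% vs 14.5% | 4.5 | 1.31 | 1.47 |
| 20% | 28.0% vs 24.0% | 4.0 | 1.17 | 1.29 |

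Example, b = 10%, s = 1: 0.10 + 0.90 × 0.10 = 0.190 and 0.10 + 0.90 × 0.05 = 0.145; the difference is 0.045 and the ratio 1.31.

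With e = 8% and 5% at b = 10% and s = 1, the rates are 17.2% and 14.5%, so 3.0 points become 2.7.

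As a gauge of clarity only, since no test is planned, two-sided 5% power at 450 per arm for 10% against 5% is 81% with b = 0. Under full persistence it becomes 72%, 59%, 44% and 28% for the four rows. For a new-onset count restricted to baseline-negative subjects it is 81%, 79%, 77% and 72%. With uninformative baseline status, the all-subject count stays at 81%.

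**The case against.** The strongest reply is that the contradiction is a one-word slip with a clear intent. Two specific statements restrict orthostatic values to observed summaries, and one word in a list says otherwise, so most analysts would follow the restriction. That is probably right about intent. The text still needs correcting, and the choice still belongs in SAP 12.

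Three stronger readings are tempting, and the documents do not support them.

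- *The SAP breaches Protocol 9.8.4.1.* A reader might infer this from the protocol's wording about each vital sign. But supine and standing changes are kept, and the protocol never names the supine-to-standing difference as an analysis variable. The secondary endpoint, clinically significant changes in vital signs, does not name it either.
- *No baseline comparison within subjects is left.* This is false. Supine and standing changes are such comparisons. For the same subjects, the mean change in the difference equals the mean standing change minus the mean supine change, so it can be recovered from the planned tables. Only its SD, median and range are lost. SAP 10.4.1.2 also lists every subject with values indicative of depletion at any time-point.
- *The count necessarily dilutes or biases the comparison.* Dilution depends on persistence, which the documents do not give. Randomisation balances pre-existing cases on average, so neither arm is favoured. SAP 10.1 plans no safety tests.

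It is also fair to say that pre-existing cases are not hidden. Orthostatic signs are measured at Visits 1 and 2, so by-visit counts should show pre-dose prevalence by arm. What those marginal counts cannot show is which subjects changed.

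**Conclusion.** The point holds as a minor correction with one useful addition. The conflict within SAP 10.4.1 is explicit. Its practical effect is an undeclared narrowing for one derived variable.

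The cut-off count mixes new-onset with pre-existing cases, which can attenuate a descriptive contrast. Where baseline-positive subjects have the same post-dose rate in both arms, the absolute difference shrinks only by (1 - b), a loss of 2% to 20% of its size for b from 2% to 20%. The ratio shrinks more, from 2.00 to between 1.71 and 1.17 under full persistence. The loss is zero if baseline status does not predict post-dose status. These sizes rest on assumed prevalence, persistence and event rates. The primary analysis is unaffected.

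**What to change.** 1. Reconcile SAP 10.4.1 and 10.4.1.1 in one of two ways. Either delete the word orthostatic from the sentence promising change from baseline, or delete the two restrictions and summarise change from baseline in the supine-to-standing difference.
2. Declare the choice in SAP 12.
3. In the cut-off table, add a row by visit and arm counting subjects who met no cut-off at the last pre-dose assessment and meet one after dosing. Use baseline-negative subjects as the denominator.
4. Keep the all-subject count beside it.

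The cost is a few words of SAP text and one table row. The pre-dose values are already collected at Visits 1 and 2, so no new data are needed.
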